6.6 Unscheduled Visit

Additional visits, such as unscheduled visits (other than the protocol required visits), may occur as clinically warranted. In this case the subject should be managed per the site standard practice.

If a DUS is performed, the data should be reported on the eCRF. In the case no complications are observed at unscheduled DUS, 30-day DUS is not required.

If a medication or AE assessment is performed, the data should be reported on the eCRF.

If the unscheduled visit is done prior to the 30-day follow-up (FU) window (< 23 days), 30-day FU is still required, via either the site visit (if vascular complications are detected at discharge DUS and/or unscheduled DUS) or telephone contact.

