3.0 CLINICAL INVESTIGATION DESIGN

This study is the prospective, single-arm, US multi-center, descriptive study to evaluate the safety of multiple access site closure in a single vein with the Perclose SMC. A total of 35 subjects will be registered at 2 US investigational sites. All subjects must have femoral DUS at discharge and at a 30-day follow-up visit (if any access site-related vascular complications (either symptomatic/visible or asymptomatic/nonvisible), nerve injury, or infection at discharge, by either the investigator or the core laboratory). All DUS images are assessed by the independent DUS core laboratory.

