6.4 Discharge (Complication Assessment)

At the time of discharge, the investigator should assess whether the subject has symptomatic or visible access site complications. In addition, femoral DUS must be done per the Corelab Guideline in the leg or legs in which access sites were closed in all subjects registered in this study to detect asymptomatic/non-visible complications if they exist. If a complication is treated, it should also be recorded in the eCRF.

DUS images should be uploaded for Corelab analysis per Abbott's specified method within 7 days from the procedure. The core laboratory will review the images and provide their assessment to investigators to determine whether 30-day DUS is required.

The investigator should record:

- Time of DUS
- Time of Discharge

Study Name: Perclose Multi-Access DUS Trial

Clinical Investigation Plan

Access site complications:

- Femoral vein stenosis (> 50%) development at the puncture site related to closure technique
 - Requiring surgical or percutaneous repair
 - Not requiring surgical or percutaneous repair
- Deep vein thrombosis in the target limb
 - Requiring surgical or percutaneous repair
 - Not requiring surgical or percutaneous repair
- Venous bleeding, retroperitoneal bleeding
 - Requiring surgical or percutaneous repair
 - Not requiring surgical or percutaneous repair
- Venous access site injury including vessel laceration
 - Requiring surgical repair, angioplasty, stenting, ultrasound-guided compression or thrombin injection
 - Not requiring above
- Re-bleeding at the access site
 - Requiring treatment or re-hospitalization
 - Not requiring treatment or re-hospitalization
- Hematoma
 - Requiring surgical or percutaneous repair
 - Hematoma \geq 6 cm but not requiring transfusion or surgical intervention
 - None of above
- Pseudoaneurysm
 - Requiring surgical or percutaneous repair
 - Requiring thrombin injection, fibrin adhesive injection, or ultrasound-guided compression
 - Not requiring above
- AV fistula
 - Requiring surgical or percutaneous repair
 - Not requiring surgical or percutaneous repair
- Venous tear
 - Requiring surgical or percutaneous repair (major)
 - Not requiring surgical or percutaneous repair

- Venous perforation
 - Requiring surgical or percutaneous repair (major)
 - Not requiring surgical or percutaneous repair
- Arterial tear
 - Requiring surgical or percutaneous repair (major)
 - Not requiring surgical or percutaneous repair
- Arterial perforation

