 - Requiring surgical or percutaneous repair (major)
 - Not requiring surgical or percutaneous repair
- Infection
 - requiring oral, intramuscular, or intravenous antibiotics, or leading to a prolonged hospitalization (major)
 - Not requirng above (minor)
- No flow-limiting suture material
- Access site-related nerve injury
 - Persisting for > 30 days
 - Resolved \leq 30 days
- Pulmonary embolism
 - Requiring surgical or endovascular intervention and/or resulting in death, to be confirmed by CT pulmonary angiography, lung ventilation/perfusion scan (VQ scan), or autopsy
 - Not requiring or resulting above
- Other

6.5 30-day Follow-up Assessments

All subjects registered in the study must have follow-up assessments at 30 days (+/- 7 days).

If a subject has any access site-related vascular complications (either symptomatic/visible or asymptomatic/nonvisible), nerve injury, or infection at discharge, the follow-up must be done by a site visit. For those subjects who had vascular complications detected on femoral DUS at discharge, a repeat femoral DUS must be done at the 30-day visit in the leg or legs in which the vascular complication(s) was (were) found at discharge.

For a subject who does not have an access site-related vascular complication, nerve injury, or infection, 30-day follow-up can be done by telephone contact. The investigator or the designee should ask whether the subject has any signals of vascular complications. If the subject has a

susceptive signal, he/she is asked to visit the hospital for further assessment, and this site visit is regarded as the 30-day follow-up. If the telephone contact is done within the time window, it is not regarded as the deviation even though the site visit occurs outside of the window.

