6.7 Scheduled Event

CIP Activity	Baseline (within 30 days prior to index procedure)	Pre-Procedure	Procedure	Discharge	30 days (± 7 days) office visit	Unscheduled visits
Subject Medical/Clinical History (Age, Sex, Risk Factors)	✓					
Subject Informed Consent	~					
Inclusion/Exclusion Criteria	~					
Duplex Ultrasound ¹				✓	√1	√2
Concomitant Medications	✓	~		✓	✓	√2
Procedure Medications			✓			
Procedure Information			~			
Perclose Usage Information			✓			
Heparin Reversal			✓			
Adverse Events			✓	✓	✓	√2

¹ 30-day DUS is only required if a complication is observed at discharge DUS. The core laboratory will review the DUS images and provide its assessment to investigators to determine whether 30-day DUS is required.

² Unscheduled visits are to occur per site standard of care. Data to be collected if performed. Protocol deviations will not be required if not done.

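### After an early unscheduled visit, 6.6 allows telephone follow-up where 6.5 requires a site visit; separately, 3.0 states a wider 30-day DUS trigger than 6.5, 6.7 footnote 1 and 15.0

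*Combined protocol and SAP*

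**What the plan says.** All places are in the combined protocol and SAP.

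**How the 30-day contact is made.** Section 6.5 covers any access-site vascular complication at discharge, symptomatic or silent, together with nerve injury and infection. Its rule ends: "nerve injury, or infection at discharge, the follow-up must be done by a site visit". The telephone is opened only to a subject without a "vascular complication, nerve injury, or infection, 30-day follow-up can be done by telephone contact". Section 6.6 deals with a subject who has had an unscheduled visit before the 30-day window opens. For that subject, "30-day FU is still required, via either the site visit (if vascular complications are detected at discharge DUS and/or unscheduled DUS) or telephone contact".

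**When a 30-day DUS is needed.** The design section, 3.0, says "All subjects must have femoral DUS at discharge and at a 30-day follow-up visit", with a bracketed condition that lists any access-site vascular complication (symptomatic or silent) and then "nerve injury, or infection at discharge, by either the investigator or the core laboratory". In 6.5, it is subjects with a vascular complication detected on the discharge DUS for whom "a repeat femoral DUS must be done at the 30-day visit". Footnote 1 of the 6.7 schedule is exclusive: "30-day DUS is only required if a complication is observed at discharge DUS". Section 15.0 also ties the 30-day scan to the discharge DUS. Under 6.4 the core laboratory reviews the images in order to "provide their assessment to investigators to determine whether 30-day DUS is required". Section 6.6 waives the 30-day DUS after an unscheduled DUS that shows no complication.

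**The concern.** Sites have two instructions for the same subject, on two separate points.

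On contact mode, a subject with a known nerve injury, an infection or a visible groin complication is a plausible attender at an unscheduled visit. If the site then follows 6.6 as written, that subject may only be telephoned. The one question that 6.5 prescribes for the call is about signs of vascular complications; it does not mention nerve function or infection. Yet 4.2 classes access-site nerve injury lasting more than 30 days as major, and infection as major when it needs antibiotics or prolongs the hospital stay. These are outcomes for which an in-person assessment is useful.

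On imaging, the primary endpoint in 4.1 counts complications found on scheduled DUS at discharge or at 30 days. Which subjects are scanned at 30 days should therefore follow one rule at both sites.

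Section 10.6 grants no waivers and requires every deviation to be reported. The text does not settle whether a telephone contact made under 6.6, or a 30-day DUS not done after nerve injury or infection, is a deviation.

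**Working it through.** The plan gives no figure to reproduce, so the check is a comparison of the rules case by case. The only arithmetic on dates is the lower end of the window: 30 − 7 = day 23, which agrees with the cut-off in 6.6.

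Inputs: the site-visit and telephone rules in 6.5; the bracket in 6.6; the DUS conditions in 3.0, 6.5, 6.7 footnote 1 and 15.0.

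The contact columns assume an unscheduled visit before day 23 with no vascular complication on any unscheduled DUS. The DUS columns assume that no unscheduled DUS was done, because a clean one triggers the 6.6 waiver.

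| Situation at discharge | Contact, 6.5 | Contact, 6.6 as written | 30-day DUS, 3.0 | 30-day DUS, 6.5, 6.7 footnote 1, 15.0 |
|---|---|---|---|---|
| A. Vascular complication seen on DUS | visit | visit | yes | yes |
| B. Symptomatic or visible vascular complication, not seen on DUS | visit | telephone open | yes | no |
| C. Nerve injury only | visit | telephone open | yes | no |
| D. Infection only | visit | telephone open | yes | no |
| E. None of these | telephone open | telephone open | no | no |

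Contact mode: 6.5 sends A to D to a visit (4 of 4). The 6.6 bracket covers A (1 of 4). Difference: 4 − 1 = 3 situations (B, C, D).

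30-day DUS: 3.0 covers A to D (4 of 4). Sections 6.5, 6.7 footnote 1 and 15.0 each cover A (1 of 4). The difference is again B, C, D.

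Could the bracket in 3.0 qualify only the visit? The sentence would still ask for a DUS at that visit, so the mismatch remains.

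Which DUS trigger does the text favour? Three places (6.5, 6.7 footnote 1, 15.0) name the discharge DUS, and the footnote does so exclusively. Section 2.1 refers to vascular complications observed at discharge, in a sentence limited to asymptomatic or non-visible subjects; read naturally, that is also situation A. Sections 6.4 and 6.7 route the decision through core-laboratory review of images, and nothing in the plan gives that laboratory nerve-injury or infection data. Section 3.0 stands alone, and its list is the one 6.5 uses for the site visit.

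Check of the fix: with the amended bracket, A to D all go to a visit under both 6.5 and 6.6. A subject in E with a positive unscheduled DUS still goes to a visit, as 6.6 already says. With 3.0 amended, the DUS columns agree in every row.

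**The case against.** The best defence of 6.6 is that it is shorthand. It says the follow-up remains required, its bracket gives a sufficient condition and not an exclusive one, and nothing in it claims to displace 6.5. A site that simply follows 6.5 breaches neither section. This stands to the extent that a reader who infers that the two sections cannot both be obeyed goes too far. It does not remove the problem: the bracket states a condition that differs from 6.5, offers the telephone as the alternative, and no text says that 6.5 prevails.

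A second defence is that 6.6 is a deliberate special rule for subjects already seen in person, like its DUS waiver, which is not challenged here. The two differ. The waiver states expressly that a requirement falls away, after a clean result on the same examination. The contact rule states no such release, and a clean DUS says nothing about nerve injury or infection.

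On imaging, the defence is that 3.0 is an overview that has compressed two 6.5 rules into one sentence. This is persuasive and shapes the fix. A reader might infer that the intended trigger cannot be determined; the documents do not support that, for the reasons given in the comparison above.

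It is also fair that one core laboratory serves both sites and that protocol training is mandatory (10.4.1). Different imaging practice at the 2 sites is a possibility left open by the text, not something shown to occur.

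**Conclusion.** The concern holds as two wording conflicts worth correcting. As written, 6.6 permits a telephone contact in three discharge situations where 6.5 requires a visit. Section 3.0 states a 30-day DUS trigger wider than the DUS-based one that the rest of the text supports.

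The size is small. The contact problem needs situation B, C or D at discharge, an unscheduled visit before day 23, and no DUS-detected vascular complication. The documents give no rates from which to derive a number, so the statement that very few of the 35 subjects would be affected is a judgement. The three-of-four count describes situations in the text, not a share of subjects.

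Two stronger inferences should be resisted. First, a reader might infer that the primary result is compromised. Situation B is symptomatic or visible, and 4.1 excludes such complications from the primary analysis. At most, the wider trigger in 3.0 would add 30-day scans in subjects with nerve injury or infection alone. The study is descriptive, with no hypothesis test (8.6) and no success criterion (8.7). Second, a reader might infer that 30-day outcomes are lost after a telephone contact. Adverse events are still collected through the 30-day follow-up (6.7, 7.3.1); what is lost is the in-person assessment that 6.5 requires.

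The gain from correction is in-person ascertainment of nerve injury and infection at 30 days, and one imaging rule at both sites.

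**What to change.** 1. In 6.6, replace the bracket with: *if the subject meets the 6.5 site-visit criteria, or a vascular complication is detected on unscheduled DUS*.

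2. In 3.0, separate the two conditions, for example: *Every subject has a femoral DUS at discharge. A 30-day site visit follows any access-site vascular complication (symptomatic, visible or silent), nerve injury or infection found at discharge. Repeat DUS at that visit is required when a vascular complication was detected on the discharge DUS, unless an unscheduled DUS has since shown no complication (6.6).*

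The DUS conditions in 6.5, 6.7 footnote 1 and 15.0 can stay as they are, and so can the 6.6 waiver.

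The cost is one bracket and one sentence in an amendment. An occasional telephone contact becomes a visit that 6.5 already requires, and no scan is added. Compared with 3.0 read literally, subjects in situations B to D no longer have a mandatory 30-day DUS. They are still seen in person, and 15.0 describes DUS for symptomatic or suspected vascular complications as standard practice.

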6.7 Scheduled Event

CIP Activity	Baseline (within 30 days prior to index procedure)	Pre-Procedure	Procedure	Discharge	30 days (± 7 days) office visit	Unscheduled visits
Subject Medical/Clinical History (Age, Sex, Risk Factors)	✓					
Subject Informed Consent	~					
Inclusion/Exclusion Criteria	~					
Duplex Ultrasound ¹				✓	√1	√2
Concomitant Medications	✓	~		✓	✓	√2
Procedure Medications			✓			
Procedure Information			~			
Perclose Usage Information			✓			
Heparin Reversal			✓			
Adverse Events			✓	✓	✓	√2

¹ 30-day DUS is only required if a complication is observed at discharge DUS. The core laboratory will review the DUS images and provide its assessment to investigators to determine whether 30-day DUS is required.

² Unscheduled visits are to occur per site standard of care. Data to be collected if performed. Protocol deviations will not be required if not done.

7.0 ADVERSE EVENTS

All vascular complications must be recorded as adverse events. In addition to vascular complications, serious adverse events (SAE) and device-related adverse events (adverse device effect) must be recorded in the CRF. Any Device Deficiency/Device Malfunction must also be recorded. Additional reporting criteria are listed under 7.3 Adverse event reporting.

7.1 Definitions

7.1.1 Adverse Event

An adverse event (AE) is any untoward medical occurrence, unintended disease or injury, or untoward clinical signs (including abnormal laboratory findings) in subjects, users, or other persons, whether or not related to the medical device under investigation.

- Note 1: This definition includes events related to the medical device under investigation or the comparator.
- Note 2: This definition includes events related to the procedures involved.
- Note 3: For users or other persons, this definition is restricted to events related to medical devices under investigation.

7.1.2 Serious Adverse Event

If the AE meets any of the criteria below, it is regarded as a serious adverse event (SAE).

- a) Led to a death,
- b) Led to a serious deterioration in the health of the subject, that either resulted in
 - 1. a life-threatening illness or injury, or
 - 2. a permanent impairment of a body structure or a body function, or
 - 3. in-subject hospitalization or prolongation of existing hospitalization, or
 - 4. medical or surgical intervention to prevent life-threatening illness or injury or permanent impairment to a body structure or a body function.
 - 5. chronic disease
- c) Led to fetal distress, fetal death, or a congenital abnormality or birth defect.

Note: A planned hospitalization for pre-existing conditions without a serious deterioration in health, is not considered to be an SAE.

7.1.3 Device Deficiency/Device Malfunction

Device deficiency is defined as an inadequacy of a medical device related to its identity, quality, durability, reliability, safety or performance, such as malfunction, misuse or use error, and inadequate labeling. This includes the failure of the device to meet its performance

Study Name: Perclose Multi-Access DUS Trial

Clinical Investigation Plan

specifications or otherwise perform as intended. Note: Performance specifications include all claims made in the labeling of the device.

A device malfunction is the failure of a device to meet its performance specifications or otherwise perform as intended when used in accordance with the instructions for use.

7.2 Device Relationship

Determination of whether there is a reasonable possibility that an investigational product or device under investigation caused or contributed to an AE is to be determined by the Investigator and recorded on the appropriate CRF form. Determination should be based on an assess temporal relationships, evidence of alternative etiology, medical/biologic plausibility, and subject condition (pre-existing condition).

7.2.1 Unanticipated (Serious Adverse) Device Effect [U(S)ADE]

Unanticipated serious adverse device effect (USADE) refers to any serious adverse effect on health or safety or any life-threatening problem or death caused by, or associated with, a device, if that effect, problem, or death was not previously identified in nature, severity, or degree of incidence in the investigational plan or application (including a supplementary plan or application), or any other unanticipated serious problem associated with a device that relates to the rights, safety, or welfare of subjects.

7.3 Adverse Event and Device Deficiency/Device Malfunction Reporting

7.3.1 Adverse Event (AE) Reporting

In this study, all vascular complications (regardless of the seriousness), all serious adverse events, procedure-related adverse events, and adverse device effects related to Perclose SMC must be reported.

Safety surveillance and reporting starts when the first Perclose SMC enters the subject's vasculature and will continue until a 30-day follow-up visit has been performed, unless the subject is deceased, or the subject withdraws from the clinical study. Adverse events will not be collected on de-registered subjects (unless specifically required by the CIP or requested by the regulatory authority). Safety surveillance and reporting will continue until sites perform the last follow-up visit, the subject is deceased, the subject concludes participation in the clinical investigation, or the subject withdraws from the clinical investigation. Sites will collect all adverse event data, including deaths and device deficiency data (if applicable), throughout the period defined above and will report these events to the Sponsor on a CRF. Sites should update additional information regarding an adverse event on the appropriate CRF.

Unchanged, chronic, non-worsening, or pre-existing conditions are not AEs and should not be reported.

The investigator must report all SAEs to the Sponsor as soon as possible but no later than outlined below.

Clinical Site	Reporting timelines
All Sites	SAEs must be reported to the Sponsor no later than 3 calendar days
	from the day the site personnel became aware of the event or as per the investigative site's local requirements, if the requirement is more stringent than those outlined above.

The Sponsor will provide an offline form to allow the investigator to report SAEs in the event the entry cannot be made in the Electronic Data Capture (EDC). This does not replace the EDC reporting system. Sites should still enter all information in the EDC system as soon as feasible.

The date the site staff became aware the event met the criteria of an SAE must be recorded in the source document. The Investigator will further report the SAE to the local IRB according to the institution's IRB reporting requirements.

Adverse Device Effect (ADE)

An adverse event related to the use of an investigational medical device.

This definition includes adverse events resulting from insufficient or inadequate instructions for use, deployment, implantation, installation, or operation, or any malfunction of the investigational medical device.

This definition includes any event resulting from the use error or from intentional misuse of the investigational medical device.

7.3.2 Unanticipated Serious Adverse Device Effect (USADE) Reporting to Sponsor and IRB

The Sponsor requires the Investigator to report any USADE to the Sponsor within 3 calendar days of the investigator's knowledge of the event, unless local requirements are more stringent, and to the IRB/EC per IRB/EC requirements.

7.3.3 Device Deficiency/Malfunction Reporting

All device deficiencies/malfunctions for the investigational device must be reported on the appropriate eCRF form. Device deficiencies/malfunctions must be reported to the Sponsor no later than 3 calendar days from the day the site personnel became aware of the event or as per the investigative site's local requirements if the requirement is more stringent than those outlined.

The device, if not implanted or not remaining in the subject, should be returned to the Sponsor.

Device deficiencies/malfunctions should be reported to the IRB per the investigative site's local requirements.

An offline form will be made available to allow the investigator to report device deficiencies/malfunctions in the event that the entry cannot be made in the EDC system. This does not replace the EDC reporting system. All information should still be entered into the EDC system as soon as feasible.

In case a device deficiency/malfunction occurred before the subject registration or in the deregistered subject, the device deficiency should be reported through the Sponsor's standard Abbott Vascular reporting channel.

